**H2.3:** The overall effects of MET treatment on SGA adherence will be mediated by degree of weight abrogation, and this relationship will be stronger among girls than boys. We anticipate a possibly complex relationship between abrogation of weight gain (associated with MET) and SGA adherence, because weight gain may also be avoided via SGA non-adherence (at the probable cost of sub-optimal psychiatric outcomes; see Specific Aim 3). A statistical framework (marginal structural models) to accommodate this possibility is described in the Statistical Analysis Plan.

**Specific Aim 3:** Assess the overall and subgroup-specific impact of MET+LIFE vs. LIFE alone on **psychiatric symptom burden, psychotropic treatment changes, and overall and weight-related QoL**, including assessment of how these effects are mediated by MET effects on weight gain and SGA adherence.

**H3.1:** Overall, assignment to treatment with MET will be associated with lower psychiatric symptom burden, decreased risk for symptom-driven treatment changes, and greater improvements in overall and weight-related QoL than LIFE alone at both 6 and 24 months, post-randomization.

**H3.2:** (HTE): MET effects on psychiatric symptoms will be smaller in patients who meet full DSM criteria for a BSD.

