Despite SGA-related medical concerns, these medications are highly effective for treating BSD and thus, given a choice, patients and their families would prefer to effectively manage this side effect rather than change medications and risk relapse (see Significance). Nonetheless, discontinuation of SGAs or switching to a lower-risk SGA is a potential strategy to manage weight gain. Unfortunately, switching SGAs produces limited or inconsistent improvements in weight and metabolic outcomes, along with some psychiatric risk. Indeed, in the recently completed IMPACT study, youth treated with SGAs who were randomized to switching to an SGA with lower weight burden experienced significantly greater rates of psychiatric symptom exacerbation than those maintained on their original SGA with lifestyle intervention or metformin added.

**Healthy Lifestyle Interventions** promote physical activity and dietary lifestyle changes. Healthy lifestyle programs designed for youth, such as the “Healthy Eating Plan” associated with Healthworks!, developed and tested by [name] (Co-Investigator), may lead to weight loss in obese youth. However, some studies show only limited benefits and involve programs that are not easily accessible. Studies of older adolescents and adults treated with SGAs found that healthy lifestyle interventions are effective for preventing weight gain and for weight loss, respectively, as well as for improving QoL, particularly when used early in the course of SGA treatment. In general, 2-5% reduction in weight or 1-1.5 body mass index (BMI) units is reported in studies of healthy lifestyle interventions for patients with mental health disorders. However, these studies suffer from high dropout rates, small sample sizes, and short duration.

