**(See Next Page)**

**Table 2. Schedule of Events.**

The Table of Events is an approximation for when routine clinic visits might occur. In order to adhere to the pragmatic nature of the study, data will only be collected during the patient's regularly scheduled clinical visits and a participant should not be brought in exclusively to conduct study specific visits. No specific study labs will be mandated for study participation, with the exception noted above (i.e., pregnancy test) The lab tests noted in the Schedule of Events are suggested in accordance with clinical practice guidelines for patients receiving SGAs.

Measures	Visit (Approximate Months)										
	SCREEN/ BASELINE	1	2	3	6	9	12	15	18	21	24
Demographics & Clinical Characteristics (P, Y)	X										
Structured Diagnostic Assessment (K-SADS) a (C)	X										
Medication List (C)	X	X	X	X	X	X	X	X	X	X	X
Weight/Metabolic											
Body Mass Index [height and weight] (C)	X	X	X	X	X	X	X	X	X	X	X
Recommended Metabolic Labs [insulin, lipid profile, glucose, hemoglobin A1C] (C)	X b,d, e				X		X		X		X
Treatment Satisfaction											
Treatment Acceptability Questionnaire (Y)	X	X	X	X	X	X	X	X	X	X	X
Adherence											
Adapted Adherence Measure (P & Y)	X	X	X	X	X	X	X	X	X	X	X
International Physical Activity Questionnaire (P & Y)	X	X	X	X	X	X	X	X	X	X	X
Nutrition, Satiety, and Appetite Measures (P & Y)	X	X	X	X	X	X	X	X	X	X	X
MEMs Cap/ SimpleMed Pillbox Upload [300 patient subset] (C)		X	X	X	X	X	X	X	X	X	X
Mood/Anxiety											
PROMIS c Anxiety Short Form (P & Y)	X				X						X
PROMIS c Depression Short Form (P & Y)	X	X	X	X	X	X	X	X	X	X	X
PROMIS c Anger Short Form (P & Y)	X				X						X
Children's Depression-Revised/Selected Items (C)	X				X						X
Young Mania Rating Scale (C)	X	X	X	X	X	X	X	X	X	X	X
Clinical Global Impression-Severity (C)	X	X	X	X	X	X	X	X	X	X	X
Quality of Life (Weight & General)											
Body Weight, Image & Self-Esteem Evaluation, B-WISE (Y)	X				X						X

"Sizing Me Up"/"Sizing Them Up" (P & Y)	X				X						X
Height Weight Self for Viewpoint-Items 5 & 6 (wt. acceptability) (Y)	X	X	X	X	X	X	X	X	X	X	X
PROMIS c Pediatric Peer Relationships- Short Form (P & Y)	X				X						X
PROMIS c Global Health Scale (P &	X	X	X	X	X	X	X	X	X	X	X
Clinical Global Assessment Scale (C)	X	X	X	X	X	X	X	X	X	X	X
Number of School/Work Days Missed [past 30 days] (Y & P)	X	X	X	X	X	X	X	X	X	X	X

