**Other potential risks:** To guard against frustration and fatigue, questions and surveys have been carefully chosen by patients, parents, and stakeholders. However, when necessary, assessments can be divided to decrease the frustration and fatigue. In addition, research staff will be hired based on their research experience and work with children and adolescents. Lastly, patients and their parent(s)/legal guardian(s) will be advised that they do not have to participate in the study and that their participation is voluntary and refusal to participate will not impact their clinical care in any way. Their alternative to study participation is to continue to receive standard clinical care. **Additional weight gain or metabolic abnormalities:** Patients in the study will be closely monitored for weight gain and metabolic abnormalities. Clinicians, parents, or patients can discontinue assigned study treatment at any point, but will still be monitored for up to 24 month. If a patient continues to have substantial weight gain ( $> 10\%$ ) in the LIFE group, a clinician might decide to add MET to the treatment if clinically indicated. Likewise, if the patient is randomized to the MET + LIFE group and continues to have substantial weight ( $> 10\%$ ) they will have the option to continue MET and/or add another treatment or switch the patient's treatment for BSD, whichever is clinically indicated. If a participant's BMI percentile 5% (= underweight) his/her treatment with MET will be discontinued.

Although the risk of low vitamin B12 while taking MET is associated with age  $> 50$  years and having type II diabetes, we will encourage clinicians to monitor B12 levels and a CBC throughout study participation. We will educate all study-related clinicians about this potential side effect of metformin and the very rare clinical manifestations of MET-related vitamin B12 deficiency (i.e., peripheral neuropathy and pernicious anemia).

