Exacerbation of BSD is also a risk, however patients will be treated for BSD as clinical indicated and there are no restrictions on psychotropic medications use. Patients will be monitored closely by site clinicians who will use the YMRS to systematically assess manic symptoms and the PHQ-9 item #9, to assess current suicidality. Patients will remain in the study even if they require a change in treatment or psychiatric hospitalization. These events will be recorded as psychiatric symptom burden outcomes. Patients who become pregnant during their study participation will continue to be followed. We will encourage treating clinicians to discontinue metformin if it is being prescribed for study participation and to consult with the prescribing clinician prior to discontinuation, if it is prescribed by another clinician and for reasons unrelated to the study.

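### The symptom-driven treatment-change component of H3.1 is undefined, and no reason for a psychotropic change is required, so weight-driven changes may be mixed in

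*Combined protocol and SAP*

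**What the plan says.** Section A (Specific Aims) names "psychiatric symptom burden, psychotropic treatment changes" among the domains of Aim 3. H3.1 narrows the second of these and predicts "lower psychiatric symptom burden, decreased risk for symptom-driven treatment changes", together with better quality of life, at 6 and 24 months. The aim heading therefore covers psychotropic changes in general, while the hypothesis covers only those driven by symptoms.

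The counting rule is in Section G.a. That paragraph opens "Exacerbation of BSD is also a risk, however patients will be treated for BSD as clinical indicated". It then says patients stay in the study "even if they require a change in treatment or psychiatric hospitalization. These events will be recorded as psychiatric symptom burden outcomes".

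Table 2 has a clinician-completed medication list at every visit. It has no row for the reason for a change and none for psychiatric hospitalisation. Section E (screening/baseline procedures) adds six-monthly collection of treatment data, and Section G says that changes and arm switches are recorded. None of these mentions the reason.

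The protocol also expects changes made because of weight. Section B says weight and metabolic effects are a common reason for stopping an SGA, and that "discontinuation of SGAs or switching to a lower-risk SGA is a potential strategy to manage weight gain". Section G.a (additional weight gain) says that, for MET + LIFE patients who gain more than 10%, "they will have the option to continue MET and/or add another treatment or switch the" patient's BSD treatment. For the same gain in the LIFE arm, the only response it names is adding MET.

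**The concern.** Whether a change is symptom-driven is a question of cause. A drug list shows that a regimen changed and when, but not why. A patient whose mood is stable and whose SGA is changed because of weight can look the same on that list as a patient whose SGA is changed for relapse.

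The weight-driven changes are not likely to be balanced noise. They lie on the trial's own causal pathway, from MET to weight to SGA change. If they enter the outcome, an arm difference in this component could arise with no difference in psychiatric symptoms. Aim 3 also asks whether psychiatric effects are mediated by weight. A weight-driven change counted as a psychiatric event would build part of that link into the outcome.

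**Working it through.** **Step 1: can the outcome be derived from what is scheduled?**
- Needed for H3.1: a change and its cause.
- Scheduled: the medication list at every visit and treatment data every six months.
- Not found: a definition of symptom-driven, a named person who decides, a reason field, or a scheduled hospitalisation item. The analysis section models SGA regimen change through marginal structural weights, without classifying it by reason.

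**Step 2: is there a figure in the plan to reproduce?** No. The text available gives no event rate, effect size or power calculation for H3.1. What follows shows only how mixing would act.

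**Step 3: model.** Let *s* be the risk of a symptom-driven change, equal in both arms (no true effect). Let *w* be the risk of a weight-driven change in each arm, independent of the first. If all changes are counted:

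recorded rate = 1 − (1 − s)(1 − w)

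difference (MET − LIFE) = (1 − s)(w_MET − w_LIFE)

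The sign is therefore that of w_MET − w_LIFE. If the two are equal, the bias is zero.

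Inputs from the protocol: 1800 patients randomised 1:1, so 900 per arm, and about 90% retention over two years, so 0.90 × 900 = 810 per arm. All values of *s* and *w* are assumptions.

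**Step 4: one worked case.** s = 20%, w = 15% (LIFE) and 8% (MET), 900 per arm.
- LIFE: 1 − 0.80 × 0.85 = 0.320
- MET: 1 − 0.80 × 0.92 = 0.264
- Difference: −5.6 points
- SE = √(0.320 × 0.680/900 + 0.264 × 0.736/900) = 0.0214
- |z| = 0.056/0.0214 = 2.62
- Chance of two-sided p < 0.05: about Φ(2.62 − 1.96) = 74%

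**Step 5: ranges.** The last two columns give the chance of a false significant result in the direction shown.

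| Assumed w, LIFE vs MET | Assumed s | False difference (points) | 900 per arm | 810 per arm |
|---|---|---|---|---|
| 10 vs 5, 15 vs 8, 20 vs 10% | 10–30% | 3.5–9.0, favours MET | 34–99% | 31–99% |
| 5 vs 2.5, 10 vs 5, 15 vs 7.5% | 20–40% | 1.5–6.0, favours MET | 9–80% | 9–76% |
| 5 vs 10, 10 vs 15% | 20–40% | 3.0–4.0, favours LIFE | 25–49% | 23–45% |
| 5 vs 5% | 20–40% | 0 | 2.5% each way | 2.5% each way |

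If only symptom-driven changes are counted, and counted correctly, every row gives a difference of zero and the nominal error rate.

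**The case against.** A reader might infer that the plan counts any change of treatment as psychiatric worsening, and that this favours MET. The documents do not support either step.

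- **The rule in context.** The Section G.a sentence belongs to a paragraph on exacerbation of BSD and never says any change. Weight gain has its own paragraph in the same section, and H3.1 is already limited to symptom-driven changes. The passages can be read consistently. This stands: the defect is a missing qualifier and definition, not a stated rule that weight-driven switches count. Even so, the narrower reading cannot be applied to a drug list without a reason.
- **Capture of reasons.** Table 2 is a visit schedule, and the case report form is not among the documents. Section E.c allows collection from clinician notes and medical records. BMI, YMRS, CGI-S and PROMIS Depression are scheduled at every visit and give indirect information around a change. So it is not shown that reasons go unrecorded, only that nothing requires them to be recorded. Low symptom scores at a switch do not establish its cause.
- **Direction.** Fewer weight-driven switches would be expected under MET if it works as hypothesised, which would favour MET. But Section G.a names the weight-driven BSD switch only for MET + LIFE, which could favour LIFE. If MET added in the LIFE arm were itself counted as a change, the bias would run back towards MET. The sign is open.
- **Reach.** The symptom rating scales and quality-of-life measures do not depend on reason coding. This one component cannot carry all of H3.1.

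**Conclusion.** The concern holds as an undefined outcome with a plausible route to bias, confined to the treatment-change component of H3.1. The protocol hypothesises about symptom-driven changes and foresees weight-driven ones, but the data collection it describes does not require what is needed to tell them apart.

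The effect ranges from nothing, if weight-driven rates are equal across arms, to a substantial false-positive risk in either direction. The percentages rest on assumed rates, independence of the two causes and every change being counted. They show sensitivity and are not forecasts. An unknown sign does not remove the problem, because reasons not recorded at the time may not be reliably recoverable later. This is a worthwhile, inexpensive improvement, not a threat to the primary BMI z-score result.

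**What to change.** 1. At every visit, in both arms, record one coded reason for each psychotropic start, stop, switch or dose change: psychiatric symptoms, weight/metabolic, other side effect, patient or family choice, other.
2. Add a psychiatric hospitalisation item (yes/no, dates) to Table 2.
3. Reconcile Section G.a with Section A, so that only changes coded as due to psychiatric symptoms, plus psychiatric hospitalisations, count towards this component of H3.1.
4. Report weight-driven and all-cause changes by arm alongside it.

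The cost is one drop-down field and one yes/no item with dates on existing forms, a wording change, and about a minute or less of clinician time per change. No visit is added and clinical decisions are untouched. The main drawback is that an unblinded clinician judges the reason, so the coding could itself differ by arm. That is why the all-cause result should be shown beside the coded one.

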## **H. PAYMENT**

Patients and their caregiver will each be paid \$25 for visits at Screening, month 6, and month 24 for their time and effort. Also, they each will each be paid \$10 for visits at month 1, 2, 3, 9, 12, 15, 18, and 21. This totals to \$155 for the patient and \$155 for the caregiver.

## **I. SUBJECT COSTS**

Patients are expected to provide for the costs of clinical care (e.g., hospitalization costs) through standard health care payment procedures. Subjects will have no costs associated with research participation.

